Febrile neutropenia Grade 3 (ANC < 1.0 x 10  /L, single temperature of > 38.3°C or a sustained temperature of ≥ 38.0°C)	Hold dose of infigratinib until resolved to CTCAE Grade ≤ 1, then 
 
• If resolved by ≤ 7 days, ↓ 1 dose level of infigratinib.
 
• If not resolved within 7 days discontinue patient from study drug treatment.
 

Grade 4	Discontinue patient from study treatment.
Hemoglobin Grade 3 (<8.0 mg/dL – 6.5 mg/dL)	Hold dose of infigratinib until resolved to CTCAE Grade ≤ 1 or baseline, then maintain dose level
Grade 4 (< 6.5 mg/dL)	Hold dose of infigratinib until resolved to CTCAE Grade ≤ 1 or baseline, then ↓ 1 dose level.
Platelet count decreased (Thrombocytopenia) Grade 3 (PLT < 50 - 25 x 10  /L) without bleeding	Hold dose of infigratinib until resolved to CTCAE Grade ≤ 1 or baseline 
 
• If resolved in ≤ 7 days, maintain dose level of infigratinib.
 
• If resolved in > 7 days, ↓ 1 dose level of infigratinib.
 

Grade 3 (PLT < 50 - 25 x 10  /L) with bleeding or Grade 4 (PLT < 25 x 10  /L )	Hold dose of infigratinib until resolved to CTCAE Grade ≤ 1 or baseline, then ↓ 1 dose level
Investigations – Renal	

A Phase 0 Study of Infigratinib in Recurrent Glioblastoma Patients  
 Protocol 2020-08

Worst Toxicity CTCAE v5.0 Grade (unless otherwise specified)	Recommended Dose Modifications any time during a cycle of therapy
Serum creatinine Grade 1 and Pi >5.5 mg/dL and/or tCa x Pi >55 mg  /dl  and despite phosphorus lowering therapy for at least 14 days	See Table 4 Hold dose of infigratinib until resolved to CTCAE Grade ≤ 1 or baseline 
 
• If resolved in ≤ 7 days, maintain dose level of infigratinib.
 
• If resolved in > 7 days, ↓ 1 dose level of infigratinib.
 

Grade 2 (> 1.5 - 3.0 x ULN)	Hold dose of infigratinib until resolved to CTCAE Grade ≤ 1 or baseline 
 
• If resolved in ≤ 7 days, maintain dose level of infigratinib.
 
• If resolved in > 7 days, ↓ 1 dose level of infigratinib.
 

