Grade 2 and Pi >5.5 mg/dL and/or tCa x Pi >55 mg/dl and despite phosphorus lowering therapy for at least 14 days or Grade ≥ 3 (> 3.0 x ULN)	Discontinue patient from study treatment.
Investigations – Hepatic	
Blood bilirubin (patients with Gilbert Syndrome these dose modifications apply to changes in direct bilirubin only) Grade 2 (>1.5 – 3.0 x ULN)	Hold dose of infigratinib until resolved to CTCAE Grade ≤ 1 
 
• If resolved in ≤ 7 days, maintain dose level of infigratinib.
 
• If resolved in > 7 days, ↓ 1 dose level of infigratinib.
 

Grade ≥ 3 (> 3.0 x ULN)	Discontinue patient from study treatment Note: If CTCAE Grade 3 or 4 hyperbilirubinemia is due to hemolysis, then ↓ 1 dose level of infigratinib and continue treatment at the discretion of the Investigator.

A Phase 0 Study of Infigratinib in Recurrent Glioblastoma Patients  
 Protocol 2020-08

Worst Toxicity CTCAE v5.0 Grade (unless otherwise specified)	Recommended Dose Modifications any time during a cycle of therapy
AST or ALT Grade 3 ( $> 5.0 - 20.0 \times \text{ULN}$ ) without bilirubin elevation $> 2.0 \times \text{ULN}$	Hold dose of infigratinib until resolved to CTCAE Grade $\leq 1$ or baseline 
 
• If resolved in <math>\leq 7</math> days, maintain dose level of infigratinib.
 
• If resolved in <math>> 7</math> days, <math>\downarrow 1</math> dose level of infigratinib.
 

Grade 4 ( $> 20.0 \times \text{ULN}$ ) without bilirubin elevation $> 2.0 \times \text{ULN}$	Discontinue patient from study treatment
AST or ALT and Bilirubin AST or ALT $> 3.0 - 5.0 \times \text{ULN}$ and total bilirubin $> 2.0 \times \text{ULN}$ without liver metastasis or evidence of disease progression in the liver	Hold dose of infigratinib until resolved to CTCAE Grade $\leq 1$ 
 
• If resolved in <math>\leq 7</math> days, <math>\downarrow 1</math> dose level of infigratinib.
 
• If resolved in <math>> 7</math> days, discontinue patient from study treatment.
 

AST or ALT $> 5.0 \times \text{ULN}$ and total bilirubin $> 2.0 \times \text{ULN}$	Discontinue patient from study treatment
Laboratory / Metabolic disorders	

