A Phase 0 Study of Infigratinib in Recurrent Glioblastoma Patients  
Protocol 2020-08

Worst Toxicity CTCAE v5.0 Grade (unless otherwise specified)	Recommended Dose Modifications any time during a cycle of therapy
Other ocular/visual toxicity	
≥ grade 3	Hold infigratinib until resolution to ≤ grade 1 If resolution in ≤14 days, ↓ 1 dose level, otherwise discontinue infigratinib
General disorders	
Fatigue Grade 3	Hold dose of infigratinib until resolved to CTCAE Grade ≤ 1 
 
• If resolved in ≤ 7 days, maintain dose level of infigratinib.
 
• If resolved in > 7 days, discontinue patient from study treatment.
 

Other clinically significant AEs	
Grade 3	Hold dose of infigratinib until resolved to CTCAE Grade ≤ 1, then ↓ 1 dose level of infigratinib.
Grade 4	Discontinue patient from study treatment

All dose modifications should be based on the worst preceding toxicity. Once a dose has been reduced it will not be increased at a later time even if there is no toxicity. Patients who require more than two dose reductions of infigratinib will be discontinued from study drug treatment.
 
If a patient requires a dose delay of > 14 days from the intended day of the next scheduled dose of infigratinib then study treatment must be stopped.
	

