Any questions regarding the dose reduction decision should be discussed with the IBTC Safety Officer.

Dose adjustments as outlined in the table below are allowed both within a cycle and between cycles. infigratinib must be reduced sequentially by 1 dose level.

For participants requiring dose reduction(s), any re-escalation to a prior dose level is permitted only after consultation with the IBTC Safety Officer. After re-escalation, subsequent dose adjustments should be based on the dose of infigratinib that the participant is currently receiving.

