**Table 5 infigratinib dose reductions**

Dose Adjustment	Oral Dose	Frequency
0	125 mg	QD
-1	100 mg	QD
-2	75 mg	QD

A Phase 0 Study of Infigratinib in Recurrent Glioblastoma Patients  
Protocol 2020-08

If a participant receiving the 75-mg dose of infigratinib requires further dose reduction, infigratinib should be discontinued. Based on the judgment of the investigator, if a participant is receiving clinical benefit from study therapy and requires further dose reduction than what is outlined in the table above, the investigator must discuss with the IBTC Safety Officer prior to further dose reduction.

Dose omissions are allowed within a cycle. If a participant requires omission of more than 25% of doses during a cycle for tolerability, then treatment may continue if the investigator determines the participant is receiving clinical benefit.

To ensure patient safety the investigator should collect specific recommended clinical information and follow-up laboratory tests as shown below in [Table 6](#).

Details for hepatic monitoring depend upon the severity and persistence of observed laboratory test abnormalities. If a study patient experiences elevated ALT 5×ULN and elevated TBL 2×ULN, or ALT 8×ULN, liver tests, including ALT, AST, TBL, direct bilirubin, gamma-glutamyl transferase (GGT), and creatine phosphokinase (CPK), should be repeated within 3 to 5 days to confirm the abnormality and to determine if it is increasing or decreasing. If the abnormality persists or worsens, clinical and laboratory monitoring should be initiated by the investigator, based on the hepatic monitoring tests below.

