#### [6.4.1.3.3 SUPPORTIVE MANAGEMENT RECOMMENDATIONS FOR HYPERPHOSPHATEMIA](#)

---

Increases in phosphate, a pharmacodynamic effect of infigratinib, can affect the homeostasis of serum phosphorus and serum calcium. As such, within the first week of infigratinib treatment (Expansion Phase), serum phosphorus and calcium levels should be monitored and checked. Manage as clinically indicated with a low phosphate diet, dose modifications/interruption, and phosphate binders. Prophylactic use of a phosphate-binding agent is allowed on days of infigratinib administration per institutional guidelines. Per investigator's discretion, if there is no ongoing hyperphosphatemia during the week with no infigratinib treatment, use of the phosphate binder should be paused. If necessary, infigratinib dosing may be interrupted to allow for normalization of serum levels of phosphorus and calcium and then resumed at a lower dose. Also see [Table 4](#) for toxicity follow-up evaluation.

A Phase 0 Study of Infigratinib in Recurrent Glioblastoma Patients  
Protocol 2020-08

Mild to moderate elevations in serum creatinine have occurred in association with hyperphosphatemia. Subjects should be carefully monitored for electrolyte changes and early signs of renal insufficiency; dosing should be withheld until serum creatinine returns to baseline, Grade 1, or better. Additionally, SAEs of renal failure, nephropathy, and acute kidney injury have been reported. In the event of acute, severe hyperphosphatemia and clinical evidence of emerging calciphylaxis, additional phosphorus-lowering strategies, including hemodialysis, should be considered. ([QED 2019](#))

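### Section 6.1.3 gives conflicting Expansion dosing rules (re-escalation, third reduction and, less sharply, phosphorus), its Grade 1 creatinine hold is released by its own trigger, and the first-week phosphorus check is missing from the Schedule of Activities

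*Combined protocol and SAP*

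**What the plan says.** Dose modifications apply to the Expansion Cohort only; Section 6.1.3 allows none in Phase 0.

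- **Re-escalation.** Table 3 footnote: "Once a dose has been reduced it will not be increased at a later time even if there is no toxicity". Section 6.1.3, text between Tables 4 and 5: "any re-escalation to a prior dose level is permitted only after consultation with the IBTC Safety Officer". The sentence after that sets out how to adjust the dose once it has been re-escalated.
- **Third reduction.** Table 3 footnote: "Patients who require more than two dose reductions of infigratinib will be discontinued from study drug treatment". The text after Table 5 has the same default at 75 mg, then adds a case for a participant with clinical benefit: if that participant "requires further dose reduction than what is outlined in the table above, the investigator must discuss with the IBTC Safety Officer" beforehand. Table 5 names no level below 75 mg. Section 7.2 lists a third reduction among the reasons an investigator may withdraw a participant.
- **Creatinine.** The Table 3 trigger is "Grade 1 and Pi >5.5 mg/dL and/or tCa x Pi >55 mg" (units mg²/dL²), "despite phosphorus lowering therapy for at least 14 days". The action, with a cross-reference to Table 4, is "Hold dose of infigratinib until resolved to CTCAE Grade ≤ 1 or baseline": same dose if resolved within 7 days, one level lower if it takes longer. Section 6.4.1.3.3 says "dosing should be withheld until serum creatinine returns to baseline, Grade 1, or better".
- **Phosphorus.** Table 3 holds drug at >7.0–10.0 mg/dL despite phosphate-lowering therapy and gives no duration for that therapy. Table 4 raises sevelamer at >7.0–9.0 mg/dL and states a hold above 7.0 mg/dL only after at least 14 days of therapy.
- **Monitoring.** In the Schedule of Activities (Section 1.2), serum chemistry carries a 1 in each Expansion cycle column and an X at End of Study Treatment. Section 6.4.1.3.3 asks for phosphorus and calcium to be checked in the first week of Expansion treatment; the Schedule has no entry for it.

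**The concern.** These rules decide whether a participant is held, reduced, re-escalated or stopped, at up to 3 sites. Where two passages give different answers, two investigators can treat the same finding differently and each be following the protocol. The creatinine row matters most for safety: the same phosphorus condition with Grade 2 creatinine means discontinuation, so the Grade 1 row looks meant as a protective step before that point, and as written it may protect no one. Laboratory abnormalities are a secondary Expansion endpoint, so the timing of scheduled chemistry also bears on what is observed.

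**Working it through.** There is no stated figure to reproduce. The check sets the rules side by side, with simple date arithmetic.

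**1. Re-escalation.** Footnote: never. Later text: allowed after consultation, with instructions for what follows. Both cannot govern.

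**2. Creatinine.** Trigger: grade = 1 plus the phosphorus or calcium-phosphorus product condition. Release: grade ≤ 1, or baseline; either suffices.
- Since 1 ≤ 1, the release condition is true at the moment of the trigger. Minimum hold = 0 days.
- Resolution is therefore always within 7 days, so the branch for more than 7 days cannot be reached from this row.
- If creatinine rises to Grade 2, a different row applies: discontinuation if the phosphorus condition persists after 14 days of therapy, or otherwise the plain Grade 2 hold.
- The cross-reference to Table 4 adds creatinine at least weekly and phosphorus follow-up, but no restart condition. Section 6.4.1.3.3 repeats release at Grade 1.

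**3. Third reduction.**

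| Place | Rule |
|---|---|
| Table 3 footnote | Discontinue, no exception |
| Text after Table 5 | Discontinue by default; further reduction possible with clinical benefit and prior Safety Officer discussion |
| Section 7.2 | Investigator may withdraw |

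**4. Phosphorus.** Take 8.0 mg/dL on Cycle 1 Day 8, with sevelamer since Day 1: 8 − 1 = 7 days of therapy, short of 14.
- Table 3, on its face: hold, then one level lower if phosphorus is ≤5.5 mg/dL within 14 days.
- Table 4: raise sevelamer; no hold is stated yet.
- If therapy starts on Cycle 1 Day 1 as Table 4 directs, and the 14 days are not read into Table 3, the tables point different ways at >7.0–9.0 mg/dL on Days 2–14: 14 − 2 + 1 = 13 of the 21 dosing days.
- At >9.0–10.0 mg/dL before 14 days, Table 4 gives no binder step. That is a gap, not a contradiction.

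**5. Schedule.** The plain 1 is read as Day 1, because the PK row shows 1, 8, 15 in Cycles 1 and 2 and Section 6.1.2 names those as days. The sample count agrees: 1 (Phase 0 Day 1) + 8 (Day 7 series, including the 24-hour sample) + 3 × 2 (Cycles 1–2) = 15, the fifteen samples in Section 8.1.1.1.
- Dosing runs Days 1–21 of 28. Cycle 2 Day 1 is Day 29, and 29 − 21 = 8 days after the last dose, following 7 drug-free days (22–28).
- With the full permitted 7-day cycle delay: 8 + 7 = 15 days.
- Phosphate therapy starts with the midday or evening meal on Cycle 1 Day 1. Nominally, the Schedule then has no chemistry on Days 2–21 of a cycle.

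**The case against.** Only the re-escalation conflict is a flat contradiction on its face, and parts of the rest can be reconciled.

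- **Other holds exist.** A reader might infer that, at phosphorus >5.5–7.0 mg/dL, the Grade 1 creatinine row is the only hold before discontinuation. The documents do not support that. Section 6.4.1.3.3 allows dosing to be interrupted until phosphorus and calcium normalise and then resumed at a lower dose, and Table 3 separately holds plain Grade 2 creatinine. This stands, but the interruption is discretionary and does not repair the row.
- **Tables 3 and 4 may be one rule.** The hyperphosphatemia entry in Table 3 points to Table 4, which could define what failing therapy means. A reader might infer outright conflict across >7.0–10.0 mg/dL; that is too strong. Table 4 never says to keep dosing, and it is silent at >9.0–10.0 mg/dL. Still, Table 3 does not state the 14 days for phosphorus, although its creatinine rows do.
- **The third-reduction texts share a default.** True. The exception requires clinical benefit and prior Safety Officer discussion. But the footnote admits no exception and Section 7.2 makes withdrawal optional.
- **Monitoring goes beyond the Schedule.** A reader might infer that no on-drug chemistry is planned. That is wrong: Section 6.4.1.3.3 asks for the first-week check and careful electrolyte and renal monitoring, and Table 4 asks for weekly creatinine once it is raised with hyperphosphatemia. What remains is that the Schedule does not carry the first-week check.
- **Oversight.** Table 3 is headed as recommendations, dose-reduction questions go to the Safety Officer, and a DSMB meets at least semiannually. The footnote's wording is nevertheless mandatory.

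**Conclusion.** The point holds as a defect in the stated dosing rules and should be fixed. Two parts are firm: the re-escalation contradiction, and the Grade 1 creatinine hold whose literal minimum is 0 days. The third-reduction inconsistency is real but narrow. The phosphorus mismatch is softer; the figure of 13 of 21 days assumes that therapy starts on Cycle 1 Day 1 and that the 14 days are not imported into Table 3. Section 6.4.1.3.3 says only that prophylactic binder use is allowed. The monitoring point is a mismatch between the Schedule and the text, plus scheduled Day 1 samples from Cycle 2 that nominally follow the off-week.

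No primary endpoint or stated statistical figure is affected. Phase 0 has no dose modifications, so the PK endpoint is untouched, and the definition of PFS6 does not depend on these rules. A reader might also infer that laboratory abnormalities will be under-counted. Unscheduled results count too, so the documents do not allow any such effect to be shown or sized.

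**What to change.** - **Re-escalation:** choose one rule and word it identically in the Table 3 footnote and the text before Table 5.
- **Creatinine:** release the Grade 1 hold only when phosphorus is ≤5.5 mg/dL, the calcium-phosphorus product is ≤55 mg²/dL², and creatinine is at baseline or no worse than at the trigger. Align Section 6.4.1.3.3.
- **Third reduction:** state one rule in the Table 3 footnote, the text after Table 5 and Section 7.2. If the exception stays, name the level below 75 mg in Table 5, for example 50 mg, which two 25-mg capsules would give.
- **Phosphorus:** put the same hold condition, with or without the 14 days, in Tables 3 and 4, and add a binder step for >9.0–10.0 mg/dL.
- **Schedule:** enter the first-week phosphorus and calcium check. The Cycle 1 Day 8 visit (±1 day) could carry it if Section 6.4.1.3.3 is reworded to match.
- **Optional:** add chemistry at the existing Day 8 and Day 15 visits of Cycles 1–2. Settle the phosphorus rule first, because Day 8 falls where the two tables differ.

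The cost is a wording amendment and one Schedule entry. Choosing the phosphorus rule without the 14 days may bring more early holds and one-level reductions. The optional chemistry is 2 visits × 2 cycles = 4 panels per participant: 40 for the 10 Expansion participants expected (50% of 20), and at most 80 if all 20 enter. PK blood is already drawn at those visits. It would not cover Cycle 3 onward.

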**Table 4 Toxicity Follow-up Evaluation**

Toxicity	Follow-Up Evaluation
Metabolic (hyperphosphatemia)	
Serum phosphorus lowering therapy consisting of dietary phosphate intake restriction and oral phosphate binders should be applied as follows:
 
Calcium-containing phosphate binders are not recommended.
 
Starting Cycle 1 Day 1 (beginning with the midday or evening meal on C1D1):
 
 
• Restriction of dietary phosphate intake to 600 – 800 mg/day, if BMI ≥ 21kg/m^2.
 
• Sevelamer 1 tablet (800mg) per meal; i.e. 3 x 800 mg/day.
 

A Phase 0 Study of Infigratinib in Recurrent Glioblastoma Patients

Protocol 2020-08

	
If serum Pi > 5.5 – 7.0mg/dL:
 
 
• Increase the dose of sevelamer up to 1200mg tid with meals
 
 
If serum Pi > 7.0mg – 9.0mg/dL
 
 
• Increase the dose of sevelamer up to 1600mg (2 tablets per meal) tid with meals
 
 
If serum phosphorus increases > 7.0mg/dL despite phosphorus lowering therapy given for at least 14 days, the infigratinib dose should be held and then dose subsequently reduced. All patients will continue to be followed until resolution to serum phosphorus ≤ 5.5 mg/dL or baseline or stabilization.

Renal	
If serum creatinine CTCAE Grade ≥ 1 has been demonstrated in conjunction with hyperphosphatemia, this parameter must be repeated at least weekly until resolution. 24-hour urine collection should also be obtained for total phosphate, calcium, protein and creatinine clearance within weekly intervals. Ultrasound examination of the kidneys should be performed as indicated to evaluate de-novo calcifications until resolution or stabilization of creatinine.

As a general approach, based on the risk/benefit balance assessment per the investigator: for a participant who experiences a new episode of Grade 3 hematological toxicity after more than 8 weeks following the last episode of same Grade 3 hematological toxicity, the investigator may consider resuming the participant on the same drug dose if the participant satisfies the following conditions:

- The participant showed stable hematological counts (≤Grade 2) during that time frame
- In the absence of any infectious sign or risk factor
- The participant is getting benefit from study treatment.

Any questions regarding the dose reduction decision should be discussed with the IBTC Safety Officer.

Dose adjustments as outlined in the table below are allowed both within a cycle and between cycles. infigratinib must be reduced sequentially by 1 dose level.

For participants requiring dose reduction(s), any re-escalation to a prior dose level is permitted only after consultation with the IBTC Safety Officer. After re-escalation, subsequent dose adjustments should be based on the dose of infigratinib that the participant is currently receiving.

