**Table 3 Dose adjustments for infigratinib-related toxicity**

Worst Toxicity CTCAE v5.0 Grade (unless otherwise specified)	Recommended Dose Modifications any time during a cycle of therapy
Cardiac disorders	
Cardiac - Prolonged QTcF interval Grade 1 and 2 : QTcF $\geq$ 481msec and $\leq$ 500 msec (asymptomatic)	Maintain dose level of infigratinib ECG assessments should be performed for 2 additional cycles at the same frequency as in cycle 1, or as clinically indicated 

• If ECG assessments show no QTcF <math>\geq</math> 481 msec, for subsequent cycles ECG monitoring will be performed as per visit schedule.

• If ECG assessments are still abnormal (QTcF

○ <math>\geq</math> 481 msec and <math>\leq</math> 500 msec), then ECG

○ Monitoring must continue at the same frequency as in cycle 1 for all subsequent cycles.

A Phase 0 Study of Infigratinib in Recurrent Glioblastoma Patients

Protocol 2020-08

Worst Toxicity CTCAE v5.0 Grade (unless otherwise specified)	Recommended Dose Modifications any time during a cycle of therapy

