Asymptomatic amylase and/or lipase elevation Grade 3 ( $> 2.0 - 5.0 \times \text{ULN}$ )	
 
• Hold dose of infigratinib until resolved to CTCAE Grade <math>\leq 2</math>.
 
• <math>\downarrow 1</math> dose level of infigratinib
 
 
Note: A CT scan or other imaging study to assess the pancreas, liver, and gallbladder must be performed within 1 week of the first occurrence of any CTCAE <math>\geq</math> Grade 3 amylase and/or lipase.
 
If asymptomatic CTCAE Grade 2 elevations of lipase and/or amylase occur again at the reduced dose, patients will be discontinued permanently from study treatment.

Grade 4 ( $> 5.0 \times \text{ULN}$ )	Discontinue patient from study treatment
Hyperphosphatemia Serum phosphorus $> 5.5 - 7.0 \text{ mg/dL}$	See Table 4 Maintain dose level of infigratinib, but modify phosphate lowering therapy

A Phase 0 Study of Infigratinib in Recurrent Glioblastoma Patients

Protocol 2020-08

Worst Toxicity CTCAE v5.0 Grade (unless otherwise specified)	Recommended Dose Modifications any time during a cycle of therapy
Serum phosphorus >7.0 – 10.0 mg/dL despite phosphate lowering therapy	
Hold infigratinib dose until resolved to serum phosphorus <math>\leq</math> 5.5 mg/dL
 
 
if resolved by <math>\leq</math> 14 days after suspending infigratinib, <math>\downarrow</math> 1 dose level
 
if does not resolve within 14 days of suspending infigratinib, discontinue patient from the study.
 

Serum Pi $>$ 10.0 mg/dL	Discontinue patient from study treatment
Hypercalcemia Serum calcium grade 2	Hold infigratinib dose until resolved to grade 1 or baseline: 
 
if resolved <math>\leq</math> 7 days after suspending infigratinib, maintain dose level
 
if resolved <math>></math> 7 days after suspending infigratinib, <math>\downarrow</math> 1 dose level
 

Serum calcium $\geq$ grade 3	Discontinue patient from the study
Nervous system disorders	
Neurotoxicity Grade 2	Omit dose of infigratinib until resolved to CTCAE Grade $\leq$ 1, then $\downarrow$ 1 dose level of infigratinib
Grade $\geq$ 3	Discontinue patient from study drug treatment
GI disorders	
Pancreatitis Grade $\geq$ 2	Discontinue patient from study drug treatment

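### Tables 3 and 4 give different triggers for holding and reducing infigratinib when phosphorus exceeds 7.0 mg/dL: no minimum time on phosphate lowering therapy in one, at least 14 days in the other

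*Combined protocol and SAP*

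**What the plan says.** Section 6.1.3 confines dose modification to the Expansion Cohort; Phase 0 has none.

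**Table 3** is headed "Recommended Dose Modifications any time during a cycle of therapy". Its hyperphosphatemia entry has a row that starts above 7.0 mg/dL and runs to "10.0 mg/dL despite phosphate lowering therapy". The action is to hold until phosphorus is 5.5 mg/dL or lower. If that takes no more than 14 days from suspension, the dose drops one level; otherwise the patient is discontinued. Above 10.0 mg/dL, treatment is discontinued.

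**Table 4** starts dietary restriction and sevelamer on Cycle 1 Day 1. For phosphorus above 7.0 and up to 9.0 mg/dL its step is "Increase the dose of sevelamer up to 1600mg (2 tablets per meal) tid with meals". It then says that if phosphorus exceeds 7.0 mg/dL "despite phosphorus lowering therapy given for at least 14 days, the infigratinib dose should be held and then dose subsequently reduced".

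**Section 6.4.1.3.3** asks that "within the first week of infigratinib treatment (Expansion Phase), serum phosphorus and calcium levels should be monitored and checked", and continues: "Manage as clinically indicated with a low phosphate diet, dose modifications/interruption, and phosphate binders".

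**The concern.** Two tables in the same section prescribe the same action for the same abnormality under different conditions. A site using Table 3 acts on the first value above 7.0 mg/dL in a patient already on a binder. A site using Table 4 may raise sevelamer and continue at full dose until 14 days of therapy have passed.

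Either error has a cost. Section 6.4.1.3.3 associates hyperphosphatemia with creatinine rises and also reports serious renal events with the drug, so delay is not clearly harmless. An unneeded reduction is hard to undo. Table 3's closing note rules out a later increase, and the text after Table 4 allows re-escalation only after consulting the Safety Officer. Up to 3 sites may enroll, so practice could differ between them.

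**Working it through.** This is a comparison of text; there is no planned figure to reproduce.

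**1. Actions before 14 days of phosphate lowering therapy**

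| Phosphorus (mg/dL) | Table 3 | Table 4 |
|---|---|---|
| >5.5 to 7.0 | keep dose, modify binder | sevelamer up to 1200 mg three times daily |
| >7.0 to 9.0 | hold, then reduce one level | sevelamer up to 1600 mg three times daily; hold not triggered |
| >9.0 to 10.0 | hold, then reduce one level | no step stated |
| >10.0 | discontinue | no step stated |

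From 14 days on, the two tables agree for values above 7.0 and up to 10.0 mg/dL. The disputed zone is therefore 10.0 − 7.0 = 3.0 mg/dL wide, before 14 days. Table 4's sevelamer step covers 9.0 − 7.0 = 2.0 of it. The top 10.0 − 9.0 = 1.0 mg/dL has no Table 4 step.

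**2. Does Table 3 contain a hidden 14-day condition?** The 14 days in its phosphorus row is the time allowed for resolution after infigratinib is suspended, not time on a binder before the hold. Where Table 3 wants a run-in, it writes one: its serum creatinine rows include the condition "despite phosphorus lowering therapy for at least 14 days". The phosphorus row does not.

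**3. Is the zone reached at a protocol-directed check?** Therapy starts at the midday or evening meal on Cycle 1 Day 1, so 14 days is reached at about Day 15 at the earliest. The first-week check falls at most about 7 days in, and 7 < 14. For example, 8.0 mg/dL at that check meets Table 3's trigger and not Table 4's. The Schedule of Activities puts Expansion chemistry on Day 1 of each cycle and sets no further Cycle 1 recheck. For that reason I do not count doses given between the two triggers.

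**4. Cost of the hold-and-reduce path** (Table 5: 125, 100, 75 mg)

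- Reduction: (125 − 100)/125 = 25/125 = 20%.
- Per full cycle: 21 × 125 = 2,625 mg against 21 × 100 = 2,100 mg, a difference of 525 mg.
- It uses 1 of 2 allowed reductions.

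**5. Number exposed.** Sections 9.1 and 9.2 plan 20 Phase 0 participants, with 50% expected in the Expansion Cohort: 0.50 × 20 = 10.

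**6. A related mismatch.** Table 4 says that dietary restriction and "oral phosphate binders should be applied as follows", starting on Cycle 1 Day 1. Section 6.4.1.3.3 only permits prophylactic binders, according to institutional guidelines. If a site starts a binder later, Table 4's 14-day clock also starts later.

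**The case against.** The best counter-reading is that the tables work together. Table 3's hyperphosphatemia entry refers the reader to Table 4. Only Table 4 spells out what phosphate lowering therapy consists of, so one could read the pair as: escalate the binder first, then hold and reduce if 14 days of it fail. This is possible, but no sentence says it. It leaves values above 9.0 and up to 10.0 mg/dL before day 14 with no step, and it sits awkwardly with Table 3 writing out the 14 days for creatinine but not here.

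Several other points stand and limit the size of the concern:

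- Table 4 does not forbid an earlier hold, so a site that holds and also raises sevelamer complies with both tables.
- The tables give different express actions only from >7.0 to 9.0 mg/dL. Above that, Table 3 is the only stated instruction before day 14.
- On Table 4's schedule, the occasions in Cycle 1 are mainly the first-week check and unscheduled tests.
- The 525 mg per cycle is lost only if extra sevelamer alone would have worked, because both tables end in hold-and-reduce if phosphorus stays high.
- Table 3's actions are recommendations, interruption is permitted when clinically indicated, and dose-reduction questions go to the Safety Officer.

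These safeguards lower the risk, but none of them states the rule. The binder mismatch in step 6 is the weaker point: Section 6.4.1.3.3 may only be limiting prophylaxis to dosing days, and its paragraph ends by pointing to Table 4.

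**Conclusion.** The concern holds. The two tables state different triggers for the same hold and reduction, and nothing in the protocol settles which applies. The conflict covers values above 7.0 and up to 10.0 mg/dL with under 14 days of phosphate lowering therapy, and the first-week check falls within that period. It affects about 10 participants if the protocol's 50% estimate is right. The protocol gives no rate of values above 7.0 mg/dL, so the number of affected decisions cannot be estimated. No endpoint definition or statistical figure changes. The issue is patient safety and consistent dosing across sites, and it should be fixed, since compliance should not depend on which table a site reads. The timing argument assumes that therapy starts on Cycle 1 Day 1 as Table 4 directs; a later start lengthens the disputed period.

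**What to change.** State one trigger in both tables.

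- **Default:** let Table 3 govern. It is the dose-adjustment table and, for hyperphosphatemia, the more protective rule. Remove the 14-day condition from Table 4's hold sentence, say that the sevelamer increase accompanies the hold, and extend that sevelamer step from 9.0 to 10.0 mg/dL.
- **If the sponsor intends a 14-day run-in:** write it into Table 3's row for values above 7.0 and up to 10.0 mg/dL instead.
- **Secondary:** make Section 6.4.1.3.3 agree with Table 4 on whether sevelamer from Cycle 1 Day 1 is expected or optional.

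The cost is amendment wording. Under the default there may also be some earlier holds. Each that resolves in time is followed by a one-level reduction that uses one of the two allowed and can be reversed only after consulting the Safety Officer.
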